9.2.5. Bone Marrow Examination

Bone marrow assessments to be performed locally and centrally are summarized in [Table 6](#).

Table 6: Bone Marrow Testing

	Local Testing	Central Testing
Screening Bone marrow aspirate/biopsy	Disease characterization (morphology and either immunohistochemistry, immunofluorescence, or flow cytometry). Cytogenetics by FISH (preferred) or karyotyping.	If a fresh bone marrow aspirate is collected at Screening, a portion will be sent to a central laboratory for biomarker evaluation.
CR, sCR Bone marrow aspirate or biopsy (or both)	For response confirmation, additional bone marrow aspirates or biopsies (or both) will be performed locally (Disease characterization [morphology and either immunohistochemistry, immunofluorescence, or flow cytometry]) to confirm sCR or CR. For sCR: immunohistochemistry, immunofluorescence (requires kappa/lambda ratio from analysis of ≥ 100 cells) or 2- to 4-color flow cytometry.	
Disease Progression Bone marrow aspirate or biopsy (or both)	Not applicable	If feasible, a bone marrow aspirate may be collected from subjects at disease progression to evaluate mechanisms of daratumumab resistance.

CR=complete response; FISH=fluorescence in situ hybridization; sCR=stringent complete response

9.2.6. Assessment of Lytic Bone Disease

A complete skeletal survey (including skull, entire vertebral column, pelvis, chest, humeri, femora, and any other bones for which the investigator suspects involvement by disease or the local standard of care imaging, [eg, low-dose CT]) is to be performed and evaluated at the study site during the Screening Phase. The same methodology used at Screening should be used throughout the study for comparison purposes. During the Treatment Phase and before disease progression is confirmed, x-rays should be performed to document response or progression whenever clinically indicated based on symptoms. Magnetic resonance imaging (MRI) or low-dose CT are acceptable methods for evaluation of bone disease and may be included at the discretion of the investigator (see the disease response criteria in [Table 5](#)). If a radionuclide bone scan was used at Screening in addition to the complete skeletal survey, then both methods must be used to document disease status. These tests must be performed at the same time. However, a radionuclide bone scan does not replace a complete skeletal survey.

Sometimes subjects present with disease progression manifested by symptoms of pain due to bone changes. In these cases, disease progression may be documented by skeletal survey or other radiographs, depending on the symptoms that the subject experiences. If the diagnosis of disease progression is obvious by radiographic investigations, then no repeat confirmatory x-rays are necessary. In instances where changes may be more subtle, a repeat x-ray may be needed in 1 to 3 weeks.

9.2.7. Documentation of Extramedullary Plasmacytomas

Sites of known extramedullary plasmacytomas must be documented during the Screening Phase. Clinical examination or MRI may be used to document extramedullary sites of disease. Computed tomography scan evaluations are an acceptable alternative if there is no

contraindication to the use of IV contrast. Positron emission tomography scan or ultrasound tests are not acceptable to document the size of extramedullary plasmacytomas.

For subjects with a history of plasmacytomas, extramedullary plasmacytomas should be assessed at Screening by clinical examination or radiologic imaging. They should also be assessed to confirm response, disease progression, or as clinically indicated.

To qualify for PR or better, the sum of products of the perpendicular diameters of the existing extramedullary plasmacytomas must have decreased by at least 50%, and new plasmacytomas must not have developed (see the disease response criteria in [Table 5](#)). To qualify for CR or better, all extramedullary plasmacytomas must have resolved. To qualify for disease progression, either the sum of products of the perpendicular diameters of the existing extramedullary plasmacytomas must have increased by at least 50% or a new plasmacytoma must have developed. In the cases where not all existing extramedullary plasmacytomas are reported, but the sum of products of the perpendicular diameters of the reported plasmacytomas have increased by at least 50%, this will also qualify as disease progression.

9.3. Pharmacokinetics and Immunogenicity

9.3.1. Evaluations

Samples to assess both the serum concentration (pharmacokinetics) of daratumumab and the generation of anti-daratumumab antibodies (immunogenicity) will be drawn from all subjects according to the Time and Events Schedule. At specified time points, venous blood samples (5 mL per sample) will be collected and the serum will be divided into 3 aliquots (1 aliquot for pharmacokinetic analysis, 1 aliquot for immunogenicity assessment [when appropriate], and 1 aliquot as a back-up).

Samples will also be collected from all subjects receiving Dara-SC (with the exception of subjects who switch from Dara-IV to Dara-SC following Protocol Amendment 4) to evaluate the immunogenicity of rHuPH20 according to the Time and Events Schedule. At specified time points, venous blood samples (5 mL per sample) will be collected and the plasma will be divided into 5 aliquots to accommodate immunogenicity screening, confirmatory, and titer assays and neutralizing antibody analysis (when appropriate) as well as volume for backup. No rHuPH20 immunogenicity samples should be collected from subjects who switch from Dara-IV to Dara-SC following Protocol Amendment 4.

The exact dates and times of blood sampling must be recorded. Refer to the Laboratory Manual for sample collection requirements. Collected samples must be stored under the specified and controlled conditions for the temperatures indicated in the laboratory manual. Samples collected for determining serum concentrations of daratumumab in this study may be retained to address questions about drug characteristics that may arise at a later time point.

9.3.2. Analytical Procedures

Samples will be analyzed to determine concentrations of daratumumab or generation of antibodies to daratumumab or rHuPH20 using validated immunoassay methods by or under the

supervision of the sponsor. For the daratumumab immunogenicity assessments, serum samples will be screened for antibodies binding to daratumumab and serum titer will also be determined from confirmed positive samples. Other immunogenicity analyses (eg, assessment of neutralizing capabilities) may be performed to further characterize the immune responses that are generated.

For the rHuPH20 immunogenicity assessments, plasma samples will be screened for antibodies binding to rHuPH20 and will be assessed in confirmatory and titer assays as necessary. Neutralizing antibody assessments may also be performed to further characterize immune responses that are generated.

9.3.3. Pharmacokinetic Parameters

The pharmacokinetic parameters are defined as:

Maximum C_{trough}	Serum predose concentration of daratumumab on Cycle 3 Day 1
C_{max}	Maximum observed concentration
C_{min}	Minimum observed concentration

Other pharmacokinetic parameters may be calculated. The Maximum C_{trough} , C_{min} , and C_{max} will be determined based on the assigned collection timepoints. If there are sufficient data, population pharmacokinetic analysis of serum concentration-time data of daratumumab may be performed and may include data from other clinical studies. If performed, details will be provided in a population pharmacokinetic analysis plan and results of the analysis will be presented in a separate report.

9.3.4. Immunogenicity Assessments

Serum from venous blood samples collected from all subjects will be assessed for the generation of anti-daratumumab antibodies (immunogenicity) according to the Time and Events Schedule. Daratumumab concentration will be evaluated at all immunogenicity time points to ensure appropriate interpretation of immunogenicity data. When both daratumumab serum concentration and immunogenicity analyses are specified, they will be performed on aliquots from the same blood draw and no additional sampling is required. Plasma samples will be collected from all subjects receiving Dara-SC (with the exception of subjects who switch from Dara-IV to Dara-SC following Protocol Amendment 4) and assessed for antibodies to rHuPH20. Procedures for sample collection, preparation, identification, storage, and shipment will be provided in the laboratory manual or equivalent document.

When an IRR occurs associated with the second administration or beyond, 1 blood sample should be obtained, if possible, from subjects in the Dara-IV group for determination of antibodies to daratumumab; in the Dara-SC group, 2 blood samples should be obtained, if possible, for determination of both antibodies to daratumumab and antibodies to rHuPH20. For subjects who switch from Dara-IV to Dara-SC, only 1 sample should be collected when an IRR occurs (to determination antibodies to daratumumab only, as antibodies to rHuPH20 will not be assessed in subjects who switch from IV to SC). No unscheduled samples need to be collected for IRRs associated with the first administration of daratumumab. Daratumumab serum concentration will also be determined from the daratumumab infusion reaction sample for the

purpose of interpreting immunogenicity data. These samples will be stored and evaluated if deemed necessary. If the infusion reaction results in treatment discontinuation, then subjects should undergo all scheduled safety and efficacy evaluations. Procedures for sample collection, preparation, identification, storage, and shipment will be provided in the Laboratory Manual or equivalent document. Samples collected for the analysis of daratumumab immunogenicity/serum concentration or rHuPH20 immunogenicity may additionally be used to evaluate safety or efficacy aspects that address concerns arising during or after the study period or for the evaluation of relevant biomarkers by the sponsor or sponsor's designee.

Subjects who discontinue treatment or withdraw from the study before confirmation of PD should have samples collected at the time of early discontinuation. Subjects who discontinue treatment will also be asked to return for immunogenicity evaluation during the Follow-up Phase. These samples will be tested by the sponsor or sponsor's designee.

9.4. Biomarkers

Samples for biomarker evaluations will be collected as specified in the Time and Events Schedule. Baseline bone marrow aspirate samples are required, if feasible, and may be subjected to DNA and RNA sequencing in order to identify multiple myeloma antigens to evaluate the generation of antigen specific immune responses, to classify subjects into high-risk molecular subgroups and to evaluate biomarkers of response and resistance to daratumumab.

In addition to planned bone marrow aspirate assessment, whole blood samples will be collected from subjects as outlined in the Time and Events Schedule for processing to plasma and peripheral blood mononuclear cells (PBMCs). These samples will be drawn from all subjects to evaluate pharmacodynamic biomarkers and to evaluate the role of the immunomodulatory mechanism of action of daratumumab in response and development of resistance. Testing may include evaluation of specific subsets of immune cells such as cytotoxic T cells, regulatory T cells, myeloid-derived suppressor cells, B cells, and NK cells. Cells may also be used for additional phenotypic and functional profiling. Previous clinical studies indicate CD8+ T cell expansion, which could be an additional mechanism for daratumumab activity. If CD8+ T cell expansion is noted in this study, then T-cell receptor sequences may be analyzed on PBMC DNA to assess clonal expansion of cytotoxic T cells. Proteomic analysis may also be used to evaluate changes in cytokines, complement proteins, soluble CD38, soluble CD59, IFN γ , granzyme, perforin, and other proteins associated with ADCC/CDC/ADCP and to evaluate potential biomarkers of response and resistance.

Stopping Analysis

Biomarker analyses are dependent upon the availability of appropriate biomarker assays. Biomarker analysis may be deferred or not performed, if during or at the end of the study, it becomes clear that the analysis will not have sufficient scientific value for biomarker evaluation, or if there are not enough samples or responders to allow for adequate biomarker evaluation. In the event the study is terminated early or shows poor clinical efficacy, completion of biomarker assessments is based on justification and intended utility of the data.

9.5. Patient-reported Outcomes

The modified-CTSQ is included in the clinical study as a measure to assess patient satisfaction with daratumumab treatment, support market access and the payer request for patient-reported outcomes (PRO) data, and assess superiority of Dara-SC. The modified-CTSQ is a secondary endpoint, not part of the statistical hierarchy. Non-inferiority will not be analyzed for this endpoint. Details on the statistical analyses will be included in the Statistical Analysis Plan.

The Cancer Therapy Satisfaction Questionnaire (CTSQ) is a 16-item PRO measure that assesses satisfaction with and preference for chemotherapy, hormonal and biological therapies based on efficacy, tolerability, and convenience. The CTSQ was developed to compare IV administration with oral medication (Abetz 2005¹; Trask 2008²³). Minimally important differences for the Satisfaction with Therapy domain were estimated using distribution based methods and based on known-group differences (Trask 2008²³). Using known groups of perceived change in cancer the average difference between groups was 3.7 points and using distribution-based methods the minimally important difference was 6.88 for 0.5 standard deviation and 5.84 for 1 standard error or measure using internal consistency reliability (Trask 2008²³).

The modified-CTSQ was adapted, with approval from the instrument developer, to contain 9 items specific to satisfaction with therapy and for comparison of IV with SC administration ([Attachment 11](#)). A domain score for Satisfaction with Therapy is calculated based on 7-items. Each item asks about the most recent cancer therapy using a 5-point verbal rating scale. The modified-CTSQ takes less than 10 minutes to complete and will be completed by the subject using paper administration.

The modified-CTSQ assesses previous administration of daratumumab, not the current visit administration. To achieve unbiased assessments, the modified-CTSQ should be administered before the subject's clinical examination, the subject receives any tests or test results, and the subject's health, health data, or emotions are discussed. The modified-CTSQ will be completed per the Time and Events Schedule until the end of the data collection period.

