Bone marrow aspirate/biopsy	Disease characterization (morphology and either immunohistochemistry, immunofluorescence, or flow cytometry), FISH (preferred), or karyotyping. Performed locally.	Up to 42 days before randomization; if a fresh aspirate, send portion to central lab for biomarker evaluation	To confirm CR (including sCR) and if feasible, at the time of disease progression. A portion of aspirate collected at PD will be sent to a central lab for evaluation of biomarkers of resistance to daratumumab.									
Skeletal survey	Low-dose whole body CT is preferred. Depending on local practice, a skeletal survey by x-ray or MRI may be used as an alternative.	Up to 42 days before randomization	As clinically indicated and per the local standard of care for imaging (X-ray, CT, or MRI). The same methodology used at Screening should be used throughout the study for comparison purposes.									
Extramedullary plasmacytomas	For subjects with a history of extramedullary plasmacytomas, lesions should be assessed by PET-CT or MRI.	Up to 42 days before randomization	To confirm MR, PR, VGPR, CR, or sCR; as well as at suspected PD and as clinically indicated per the local standard of care									
Modified-CTSQ	To be completed prior to any other study procedures at that visit.		C2	X	X	X	X		X	X		
Medical resource utilization	See Section 9.6 for details		X	X	X	X	X	X	X			
Ongoing Subject Review												
Adverse event monitoring	See Section 12 for details.		Continuous from time of ICF signature until 30 days after last study drug dose							Treatment-related serious adverse events		
Concomitant medication recording	See Section 8 for details.		Continuous from time of ICF signature until 30 days after last study drug dose									
Subsequent therapy, survival, second primary malignancy information			Continuous from first dose of study drug until end of study									

Study Day	Notes	Study Visits									
		Screening Phase	Treatment Phase (1 Cycle = 28 days)						Follow-up Phase		
			Cycles 1 & 2				Cycles 3-6		Cycles 7+	EOT	FUP ^a
-28 to -1	D1	D8	D15	D22	D1	D15	D1 ^c	Post-Treatment Week 4 +7 days	Post-Treatment Week 8 ±7 days	q16wks After PD ±14 days	

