2.1.2. Endpoints

Primary Endpoints

The co-primary endpoints of this study are:

- ORR, defined as the proportion of subjects with a PR or better according to the International Myeloma Working Group (IMWG) response criteria
- Maximum C_{trough} , defined as the serum predose concentration of daratumumab on Cycle 3 Day 1

Secondary Endpoints

- Rate of IRRs
- PFS, defined as the time from randomization to the date of disease progression or death due to any cause, whichever occurs first
- Rate of VGPR or better, according to the IMWG response criteria
- Rate of CR or better, according to the IMWG response criteria
- Time to next therapy (TNT), defined as the time from randomization to the start of the first subsequent anti-cancer therapy

- OS, defined as the time from randomization to the date of death
- Patient-reported satisfaction with therapy, defined as the mean of responses to 7 of 9 questions in the modified Cancer Therapy Satisfaction Questionnaire (modified-CTSQ)
- Duration of response, defined as date of onset of first response until date of disease progression or death
- Time to response, defined as the time from randomization until onset of first response

Refer to Section 9, Study Evaluations for evaluations related to endpoints.

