11.9. Patient-reported Outcomes

The modified-CTSQ item scores and Satisfaction with Therapy domain score will be summarized for each time point, by treatment arm and descriptively reported. Mean Satisfaction with Therapy domain score will be compared between treatment arms at each time point.

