## 9. PATIENT-REPORTED OUTCOMES

The modified Cancer Therapy Satisfaction Questionnaire (modified-CTSQ) is a patient-reported outcome (PRO) measure to assess patient satisfaction of Dara SC compared with Dara IV in support of market access and payer request for patient-reported outcomes data.

The modified-CTSQ was adapted, with approval from the instrument developer, to contain 9 items specific to satisfaction with therapy and for comparison of IV with SC mode of administration. Each item asks about the most recent cancer therapy using a 5-point verbal rating scale (see Attachment 3). The modified-CTSQ asks about previous administration of daratumumab, not the current visit administration. To achieve unbiased assessments, the modified-CTSQ should be administered before the subject's clinical examination, the subject receives any tests or test results, and the subject's health, health data, or emotions are discussed.

The modified-CTSQ is a secondary endpoint, not part of the statistical hierarchy. Non-inferiority will not be analyzed for this endpoint. Type I error control was not applied to patient-reported outcome data.

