## 9.2. Analysis Method

Analysis of PRO data will be performed on ITT analysis set. For subjects with multiple records at the same visit, the closest one to the visit date will be selected as scheduled assessment, and others will be unscheduled assessments.

At each time point for analysis, the number and percentage of modified-CTSQ assessment forms that are expected, received and missing will be tabulated by treatment group. The missing PRO assessments are defined as the expected number of assessments for a particular visit minus the actual number of assessments received for that visit, the expected number of assessments per visit will be determined by subject-level study completion status.

For each modified-CTSQ item score and SWT domain score, descriptive statistics (n, mean, standard deviation, median, and range) will be provided for each time point by treatment group. The mean difference (with its 95% CI) of SWT domain score will be calculated and compared between treatment groups at each time point.

Line plot of mean scores with standard error over time will be displayed by treatment group for each individual item score and SWT domain score.

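### The protocol gives the satisfaction questionnaire a superiority purpose, but the plan names no visit, over-time summary or decision rule that could answer it

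*Protocol*

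**What the plan says.** Protocol 9.5 gives several reasons for collecting the modified-CTSQ: to measure satisfaction, to supply data for market access and payers, "and assess superiority of Dara-SC". The next sentence limits its standing: "The modified-CTSQ is a secondary endpoint, not part of the statistical hierarchy". The section rules out a non-inferiority analysis and leaves the method to the SAP.

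The endpoint definition in Protocol 2.1.2 reads "Patient-reported satisfaction with therapy, defined as the mean of responses to 7 of 9 questions" of the questionnaire. It names no time point.

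Protocol 11.9 says that item and domain scores "will be summarized for each time point, by treatment arm and descriptively reported", and then: "Mean Satisfaction with Therapy domain score will be compared between treatment arms at each time point".

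SAP 9.2 says: "The mean difference (with its 95% CI) of SWT domain score will be calculated and compared between treatment groups at each time point". It gives no p-value, test level, key visit or summary over time. SAP 9 repeats that the endpoint is outside the hierarchy and adds: "Type I error control was not applied to patient-reported outcome data". SAP 9 states the purpose as assessing satisfaction with Dara-SC compared with Dara-IV and does not mention superiority.

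The Time and Events Schedule (Protocol Table 1) schedules the questionnaire at most dosing visits in Cycles 1 and 2, on Day 1 of later cycles, and at End of Treatment.

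**The concern.** Satisfaction is the subject of a secondary objective (Protocol 2.1.1), and its stated uses lie outside the trial report. The protocol says the instrument is there to assess superiority and sends the reader to the SAP for the method. The SAP returns a series of visit-wise intervals. If some exclude zero and others do not, nothing says which of them answers the objective. In an open-label study, the choice of visit could then be made with the results in view.

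The co-primary conclusions and the ordered secondary tests are not affected. What is at stake is whether the trial can support a clear statement about satisfaction, and how easily an isolated favourable visit could be presented as superiority.

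**Working it through.** The documents state no sample size, power or error rate for this endpoint, so there is no figure of the plan's own to reproduce.

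**Inputs**
- Level per visit: a 95% CI corresponds to 5% two-sided, or 2.5% in the direction favouring Dara-SC. This is implied by the interval; no test level is written.
- Number of visits K, read from the modified-CTSQ row of Protocol Table 1, whose columns are broken in the text: Cycle 1 Days 8, 15, 22 (3); Cycle 2 Days 1, 8, 15, 22 (4); Cycles 3 to 6 Day 1 (4); Cycle 7 Day 1 (1); End of Treatment (1). Total 3 + 4 + 4 + 1 + 1 = 13, and more for subjects treated beyond Cycle 7.
- Correlation between the visit-wise test statistics: not given. Assumed range 0 to 0.9.
- Decision rule: none is written. The calculation supposes that a reader takes any visit whose interval excludes zero in favour of Dara-SC as superiority.

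**Independent visits**
- False result favouring Dara-SC: 1 − (1 − 0.025)^13 = 0.280.
- False difference in either direction: 1 − (1 − 0.05)^13 = 0.487.

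**Correlated visits.** For exchangeable correlation ρ, simulate Z_k = √ρ·W + √(1 − ρ)·e_k, with W and e_k independent standard normal (400,000 draws). Count the draws in which the largest Z_k exceeds 1.96, or the largest |Z_k| for either direction.

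| ρ (K = 13) | Favouring SC | Either direction |
|---|---|---|
| 0 | 28.0% | 48.7% |
| 0.5 | 16.7% | 33.4% |
| 0.7 | 12.0% | 24.0% |
| 0.9 | 6.9% | 13.7% |

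If correlation instead decays with distance between visits (first-order autoregressive), the SC-favouring rate is 19.1% at 0.7 and 11.2% at 0.9. With K = 20 and exchangeable correlation it is 39.7% (ρ = 0), 14.2% (0.7) and 7.8% (0.9).

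Against the nominal 2.5%, the range for K = 13 is 0.069 / 0.025 = 2.8 to 0.280 / 0.025 = 11.2 times. Missing forms and dropout are ignored.

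**Side check on size of effect.** Protocol 9.5 equates 0.5 SD with 6.88 points, so SD = 13.76. This comes from the parent questionnaire, not the modified one. With 240 per arm and complete data, the 95% half-width at one visit is 1.96 × 13.76 × √(2/240) = 2.46 points. An observed difference between 2.46 and 3.7 would therefore exclude zero while lying below the smallest important difference quoted in 9.5 (3.7). An interval excluding zero is thus not by itself evidence of an important difference.

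**After the fix.** One prespecified contrast with a 95% CI carries 2.5% for a false result favouring Dara-SC, or 5% in both directions. Keeping all 13 visits with a Bonferroni correction would need 0.05 / 13 = 0.0038 per visit.

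**The case against.** The strongest reply is that the plan is candid. Protocol 9.5 and SAP 9 both place the questionnaire outside the hierarchy, SAP 9 disclaims type I error control, and Protocol 11.9 calls the reporting descriptive. The confirmatory family in SAP 5.1.1 (infusion-related reactions, PFS, VGPR or better, OS) does not include satisfaction. All of this stands: there is no hidden multiplicity failure.

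It is also fair that an any-visit rule is not in the documents and that a contrast is partly named. The variable, its scoring and the measure (SWT mean difference between arms) are specified; only the time point or summary is missing. A profile of visit-wise means is a legitimate descriptive display.

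The SAP, to which the protocol defers, can be read as having narrowed the purpose by leaving superiority out. That reading does not close the gap, because the current protocol (Amendment 4, dated after SAP Amendment 1) still carries the superiority clause. Standing outside the hierarchy makes a result nominal; it does not say which of 13 or more results answers the objective.

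A reader might infer that the chance of a false superiority finding is several times 5%. The documents do not support that. It requires nearly independent visits, or counting differences that favour Dara-IV. Repeated ratings by the same subjects are likely to be correlated, and at exchangeable correlations of 0.7 to 0.9 the SC-favouring rate is 12% to 7%, about 2.4 to 1.4 times 5%.

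**Conclusion.** The concern holds as a mismatch between a stated purpose and the planned analysis. Protocol 9.5 asks for an assessment of superiority, and neither document provides a visit, a summary over time or a rule with which to make one. No error rate that the plan promises is broken.

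The size is conditional. If any visit excluding zero were taken as superiority, the chance of at least one false result favouring Dara-SC would be about 7% to 28% over 13 visits, and 17% at a correlation of 0.5, against 2.5%. This rests on the reading of a broken table row, on an assumed correlation, on complete data, and on a decision rule that a reader would have to supply. The absence of a defined analysis for the purpose depends on none of these.

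The point merits a change because the fix is cheap and settles what the trial can say about satisfaction. It does not bear on the non-inferiority conclusion.

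**What to change.** In SAP 9.2 and Protocol 11.9, prespecify one contrast for the satisfaction objective. A suitable choice is the SWT treatment difference averaged over a stated set of scheduled on-treatment visits. Estimate it from one repeated-measures mixed model with treatment, visit, treatment-by-visit interaction and the three randomisation factors. The sponsor should choose the visits and give the reason. Report the contrast with its 95% CI and label it nominal, because it stays outside the hierarchy. State that visit-wise differences and single items are descriptive and do not support a superiority statement. The planned plots over time can remain, so the time course is still shown.

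If the sponsor prefers not to name a contrast, delete the superiority clause from Protocol 9.5, which brings it into line with SAP 9.

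The cost is a few sentences and, for the first option, one additional model on data already collected. The downside is that an isolated visit can no longer be presented as superiority.
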